We will request specific research data storage from UoM IT for the usage data files. Data files will be then held on The University of Manchester secure server (and backed-up as per usual UoM standards) for the purposes of analyses and will only be accessed by the DIPLOMA team. We will request providers transfer data to us on a monthly basis using this process.

Analyses: We plan to use the AMUsED (Analyzing and Measuring Usage and Engagement Data) framework¹ for evaluating digital interventions. This framework comprises three stages: 1) familiarisation with the intervention and its relationship with the captured data, 2) identification of meaningful measures of usage and specifying research questions to guide systematic analyses of usage data, and 3) preparation of datasheets and consideration of available analytical methods with which to examine the data.

We will identify core BCTs (e.g. goal setting, action planning, self-monitoring, feedback, reviewing goals, problem solving and others mentioned in the intervention specification) and identify a threshold by which each was delivered/received by service users. The raw usage data will be recoded according to this approach. For example, we will code whether the BCT is present in the intervention (yes/no) and we will code whether users engaged with that specific BCT (yes/no). Analyses will report specific BCTs and key intervention features which were (1) offered to users, and (2) which users effectively

¹ Miller S, Ainsworth B, Yardley L, Milton A, Weal M, Smith P, Morrison L. A framework for Analyzing and Measuring Usage and Engagement Data (AMUsED) in digital interventions. *Journal of medical Internet Research* 2019;21(2):e10966.

engaged in. This will allow assessment of delivery and receipt of the intervention. Reporting of these will be broken down according to digital provider.

Further, we expect providers to be collecting bodyweight data as part of the NHS DPP, as this is a requirement in the framework for the programme. If this data is collected as part of the usage data for the NHS DPP, we would like to conduct analyses to explore any relationship between BCT delivery/receipt within the intervention and bodyweight outcomes e.g. whether engagement with particular features of the digital DPP (e.g. BCTs) are linked to weight loss outcomes. DIPLOMA also has access to a Minimum Dataset (MDS) supplied by NHS England which includes a referral ID and bodyweight measurements at specific milestones recorded by the provider throughout the digital DPP. If the usage data supplied by the providers contains the same referral ID, we would like to explore conducting some analyses using the MDS linked with usage data to explore any relationship between BCT delivery/receipt within the intervention and bodyweight outcomes.

Work package 4 - Outcomes ([name])

Aims: To assess what outcomes participants achieve in the NHS DPP, and whether outcomes vary by services delivered and patient characteristics

Rationale: High quality data collection and measurement of outcomes is increasingly seen as a critical aspect of effective health care. ⁸⁷⁻⁸⁹ The NHS DPP will put in place a comprehensive protocol for data collection. Detailed analysis of this data will be critical to assessing the effectiveness of the programme in achieving improvements in well-being, behaviour change and lifestyle among those attending. Such data may provide useful feedback for providers on performance, and variation between providers, sites and professionals.

Overview of methods: This work package seeks to assess what outcomes participants achieve in the NHS DPP, and to identify which components of the NHS DPP intervention are effective, and for whom. It will identify the sources of any variation in outcomes among those who attend the NHS DPP intervention, and explore drivers of that variation.

Work package 4 will focus primarily on comparisons within the programme, and will link closely with analyses from work package 3 on Service Delivery and Fidelity. WP4 will analyse the individual level data set collected by NDPP providers to look at variation in participation, service delivery and outcomes. There will not be a comparator group, as the comparative analysis will be done more robustly in WP5. Analyses against external comparators will be considered by Work package 5.

Research question WP 4.1 - What services are delivered by NHS DPP and what is the extent of participation in the NHS DPP intervention?

Research question WP 4.2 - How does service delivery and participation in the programme vary by (a) the 4 NHS DPP providers (and any variation within provider by area) and the associated variation in content and delivery (b) between patient subgroups?

Research question WP 4.3 – What are the outcomes of patients in the NHS DPP intervention, including wellbeing score, weight change, HbA1c, and mortality?

Research question WP 4.4 – How do outcomes vary by (a) the 4 NHS DPP providers (and any variation within provider by area) and the associated variation in content and delivery (using data from work package 3) (b) between patient subgroups?

Methods: All research questions will be addressed using a minimum individual patient data set. NHS DPP have already stipulated that NHS DPP providers will be required to collect and supply this data, which will then be passed in anonymised form to the research team. The individual dataset will include 48 items, including referrer, delivery organisation, personal/demographic details, process data (including records of each session) and outcome data (Warwick-Edinburgh Mental Wellbeing Scale, weight change, and HbA1c).

Based on the NHS DPP announcement that it expects to provide 100,000 places per year by 2020 (https://www.england.nhs.uk/ourwork/qual-clin-lead/diabetes-prevention), we have made the assumption that there will be 50,000 individuals in 2017/18; 80,000 in 2018/19 and 100,000 in 2019/20, a total of 230,000 individuals.

We will match this individual patient data to service-level data on what is being provided by the providers in different areas, collected by the 'Implementation' and 'Service and Fidelity' work packages. This will be a rich individual level longitudinal dataset, that will allow patients be followed over time, through the steps of invitation, baseline assessment, enrolment, service delivery, completion, and end-of-service outcomes.

We anticipate that, like any administrative dataset, there will be error and missing data. As with other aspects of the evaluation, the DIPLOMA team will work closely with the NHS DPP to ensure that suitable processes are in place to ensure data collection is as accurate and complete as possible. We will provide feedback on missing data through our initial analyses, and follow up with providers if problems continue.

We will use descriptive statistics to assess overall outcomes, and multivariable regression methods to estimate the relationship between patient, provider and service characteristics and participation (question 4.2) or outcomes (question 4.4). For analysis, we will use multilevel modelling of individual characteristics (focusing on health inequalities – WP1) and service delivery (number of sessions attended; area/provider; and important elements of service delivery identified in WP3 (e.g. behaviour change techniques) on the outcomes collected by NDPP providers (weight, HbA1c, WEMWBs etc.). We will work closely with providers to minimise missing data, and we will report the extent of missing data. We will consider multiple imputation methods, if we assess that the data meets the assumption of NMAR.

WP4 will use the insights/models developed in the WP1-3 to influence the choice of variables in our statistical models: on health inequalities (WP1) and service delivery/fidelity (WP3). We will incorporate these to estimate their effect on participation, service delivery and outcomes for NDPP attenders.

We will produce regular reports to inform ongoing NHS DPP service delivery, drawing on exemplars such as the IAPT dataset.⁸⁷ To ensure the relevance of these reports, a detailed analysis plan will be written in advance, in negotiation with the NHS DPP, and this can be re-negotiated over the course of the project.

Timing of analysis: Analysis will be undertaken at three time points: Summer 2018 (using year 1 data, around 50,000 patients); summer 2019 (using Year 1 and 2 data, around 130,000 patients), summer 2020 (using complete dataset, around 230,000 patients). The earlier reports will focus on reporting who is invited to attend, baseline measures and enrolment, but as time progresses, we will be able to say more about the services delivered, completion rates and end-of-service outcomes.

Amendment to WP4

Non-substantial amendment

WP 4.5 Comparison of face to face and digital DPP – observational cohort study, secondary analysis

Rationale: The DIPLOMA project has been awarded additional funding to compare the face-to-face and digital delivery of the NHS Diabetes Prevention Programme (DPP), in terms of population characteristics, participation rates and health outcomes. Face-to-face and pilot digital DPP offered similar content with different delivery methods. The delivery of these two programmes at the same time offers a unique opportunity to compare face-to-face and digital delivery. This analysis will contribute to RQs 4.2 and 4.4.

Objectives:

- 1. Compare the population characteristics of those who take up the options of face-to-face and digital delivery.
- 2. Compare participation rates between face-to-face and digital delivery.
- 3. Compare the clinical effectiveness of face to face and digital delivery, among those who complete the programme

Populations

Face to face DPP was offered to adults with NDH. Digital DPP was offered to 1) adults with NDH; 2) adults who are overweight or obese. Overall, 4409 people registered for the programme during the 12 months pilot, 3612 with NDH and 797 who were obese. Of these, 2687 people provided outcome data

- 1. Choice (32.6% of registrations). Within the Digital DPP, four areas (BNSSG, Bucks, Lancs and Salford) offered patients a choice between digital and face to face. The NHSE Minimum Data Set (MDS) is available for the f2f providers in these areas, allowing a direct comparison.
- 2. Digital only (59.7% of registrations). This was delivered in areas where there was no F2F programme, but it did not last long, because F2F was gradually rolled out to all areas.
- 3. Decliners (7.7% of registrations). Only people who declined to take up the F2F programme were offered digital.

Data

Two datasets will be combined for analysis:

- Face to face DPP dataset
- 2. Digital DPP dataset

These two anonymised datasets are supplied to us by NHS England, collected from patients participating in the NHS DPP (individual characteristics, referral source, extent of participation in the DPP, and health outcomes). No personal details will be available to the research team. We already have the first dataset (face-to-face MDS, as used in the previous WP4 analysis) and NHSE have agreed to provide us with the second dataset (digital DPP). The second dataset contains similar variables, but on a different population. We are signing a Memorandum of Understanding with NHSE to cover the data sharing and we will follow the same UoM information governance procedures as our current DIPLOMA analyses.

Power calculation

HbA1c at 6 months among those taking the F2F DPP is 39.9 mmol/ml (SD 4.08). A reduction in HbA1c of 5 mmol/ml (0.5%) or more is considered to be clinically important so if the difference in the means of the two groups is less than 5 they can be regarded as having a similar effect. Assuming a standard deviation in both F2F and digital DPP of 4.08, 90% power, alpha 5% and 5-to-1 allocation of controls to cases, to observe a difference of 2 mmol/ml we would need a total of 486 people (81 digital, 405 F2F). There are 2200 digital participants with 6 month outcomes, which should provide sufficient numbers, after matching.

Missing data

Multiple imputation by fully conditional specification will be used to reduce bias due to missingness (up to 30% among covariate values in the F2F MDS).24, 25 Multiple imputation has already been applied to the F2F dataset, and a similar approach will be implemented in the digital dataset.

The analysis of clinical effectiveness will focus on completers: in both datasets, outcome data was only collected on those who stayed in the programme until the outcomes were recorded, so there will be considerable, systematic bias in terms of differences between responders and non-responders.

Analysis

1. Descriptive statistics

We will describe patient participation (registrations, starts and completion) in digital and face to face, and explore differences between digital and face to face patients.

2. Differences in participation (start and completion)

We will estimate differences in participation (registration, start and completion) between digital and face to face. Differences will be explored using three approaches

- a) Raw (uncorrected) differences in participation.
- b) Adjusted differences in participation. During DIPLOMA1 our team has already developed logistic regression models to estimate the effect of demographic variables, baseline outcomes and service characteristics on participation in the F2F DPP. We will apply those models to the combined dataset, with the addition of a variable for F2F/digital. This will allow us to estimate the effect of DPP delivery method, controlling for known differences between the two cohorts in factors at baseline.
- 3. Matched cohort study (primary analysis) A propensity score approach attempts to mitigate the effects of selection bias by balancing the available covariates between the two treatment arms, increasing the validity of the between-group comparison in an observational study. Propensity scores for each individual will be developed from a logistic regression model, estimating the probability of receiving F2F or digital, conditional on available demographic, service and administrative baseline

covariates. We will use nearest neighbour 1:5 non-replacement matching. Once the matched dataset has been developed, it will be analysed using random effects logistic regression models adjusting for baseline scores, provider and CCG.

3. Differences in clinical outcomes (weight and HbA1c)

A similar approach will be followed to that utilised to analyse differences in participation outcomes.

All approaches will be analysed using random effects linear regression models adjusting for baseline scores, provider and CCG.

Work package 5 - Comparative Effectiveness ([name] and [name])

Aims: To assess whether the NHS DPP is more effective than usual care in reducing conversion of non-diabetic hyperglycaemia to diabetes, eventually reducing diabetes prevalence in England

Rationale: Although the NHS DPP is based on a strong international evidence base, ⁴⁹ justifying the commissioning of such a large and complex programme requires rigorous scientific evidence that the programme is achieving benefits beyond those delivered by current prevention services. The roll-out of the programme makes formal randomised evaluation problematic. This work package will utilise administrative data and a range of complex statistical techniques to provide a rigorous estimate of the success of the programme in reducing conversion of non-diabetic hyperglycaemia to diabetes (incidence), and reducing the overall numbers of cases of diabetes (prevalence). Outputs from work packages 4 and 5 will complement each other and provide a complete evaluation of the outcomes of the scheme.

Overview of methods: For these analyses, we will use numerous sources of administrative data.

First, we plan to use the National Diabetes Audit (NDA), both in itself and also linked at the individual patient level to the DPP Minimum Dataset (MDS). The NDA plus MDS will provide a national-level source of data on patients with NDH, including their referral and participation in the DPP, and subsequent outcomes including diabetes diagnosis, HcA1c and BMI, across all GP practices. Initially data from the National Diabetes Audit was not considered for DIPLOMA as it lacked data on patients with non-diabetic hyperglycaemia, thus not allowing conversion to diabetes to be evaluated. That information has now been added (including retrospectively). Providing that the NDA dataset satisfies various completeness and quality checks, the NDA+MDS will be used as the primary data source.

The second major source of routine data will be the Clinical Practice Research Datalink (CPRD) GOLD, a large database of administrative primary care data. CPRD covers fewer GP practices than the NDA+MDS, though is still substantial in itself, and will become the primary data source should NDA+MDS be found not suitable. The database has been active since the 1980s with high quality data becoming available after 2000 with the introduction of the Quality and Outcomes Framework (QOF). 90 Complete data on all aspects of care (diagnoses, referrals, treatments, tests) have been collected from over 500 practices each financial year, covering approximately 7% of the UK population. 91 The CPRD GOLD population is generally representative of the UK population, especially in terms of practice and patient deprivation, although it is largely tied to a single clinical computer system (Vision), 92 and as a consequence the North-East of England is somewhat under-represented. 93 The CPRD data can be linked to Hospital Episode Statistics (HES) and Office for National Statistics (ONS) data, allowing the construction of a more complete patient journey through primary and secondary care and the mapping of causes of mortality (e.g. diabetes, cardiovascular). From October 2017, CPRD has also access to GP practices with the IT software system EMIS Web, which is used in 56% of English practices. This larger data resource, which ensures better population coverage has similar characteristics to the GOLD database described above.

A third data source will be the general practice diabetes registers as collected for the QoF, ⁹⁴ and related information about the general practices themselves. We will make use of free public health datasets from the ONS and the Health & Social Care Information Centre (HSCIC), including geographical data, 2011 census based population estimates, deprivation and rurality information, ⁹⁵ to map diabetes at a low population level and also to scale up our findings to a national level. We will also obtain point of interest data from the Ordnance Survey (OS). ⁹⁶ All these datasets will be linked at a low population level and will be used to map diabetes and non-diabetic hyperglycaemia prevalence rates and their associations with area and population characteristics nationally. Non-diabetic hyperglycaemia data in practice registers should become available after implementation of the NHS DPP nationally, and will be linked with existing datasets.

Research question WP 5.1 – What is the current epidemiology of non-diabetic hyperglycaemia and diabetes?

This work package will investigate rates and patterns of non-diabetic hyperglycaemia and its conversion into a diabetes diagnosis, to provide critical background information for the interpretation of findings related to the effects of the NHS DPP.

Methods: We will investigate the prevalence and incidence of non-diabetic hyperglycaemia using a specific list of Read codes which are routinely used in UK primary care. ⁹⁷ A preliminary analysis using CPRD shows that the use of the codes has increased considerably over time. For the latest period (April 2015 to March 2016), at least one relevant code was found in the records of 71,521 patients (1.57%), implying around 900,000 people nationally with non-diabetic hyperglycaemia.

We will also estimate the association between diabetes and non-diabetic hyperglycaemia prevalence at the practice level. We expect a strong correlation which would indicate that diabetes data can be used as a reasonable proxy in the absence of data on non-diabetic hyperglycaemia data.

From 2016-17 onwards, we will use these historical codes and the new codes that will be introduced with the NHS DPP programme to calculate and report detailed information on non-diabetic hyperglycaemia. Excluding cases with an existing diabetes diagnoses, we will calculate both the prevalence and incidence of non-diabetic hyperglycaemia over time, nationally and regionally (such as CCGs or NHS England Local Area Teams). To better understand regional variation, we will calculate age-sex standardised prevalence and incidence rates. We will use longitudinal multivariable mixed-effects regression models to identify predictors of non-diabetic hyperglycaemia from a list of relevant covariates: age, sex, deprivation and QOF comorbidities (excluding diabetes mellitus). 98 99 We will investigate changes in the characteristics of the non-diabetic hyperglycaemia populations over time, by including time interaction terms in the regression models.

We will use an interrupted time-series design² to quantify the overall effect of the introduction of the NHS DPP on the prevalence and incidence recording of non-diabetic hyperglycaemia (overall and regionally). This is a quasi-experimental design which we have applied in a number of previous studies, most notably to evaluate the impact of the QOF. ^{93 100 101} Using a mixed-effects regression model we will control for any changes in the population demographics over time, to obtain a more reliable effect estimate. ¹⁰² This design assumes a linear pre-intervention trend, which seems plausible according to our initial modelling. Nevertheless, we will statistically assess linearity and if rejected we will use alternative models with non-linear terms for prevalence of non-diabetic hyperglycaemia.

More inclusive criteria in the Health Survey for England have returned much higher prevalence estimates for non-diabetic hyperglycaemia, and we will explore implementing them to obtain more speculative estimates through which to conduct sensitivity analyses (i.e. based on HbA1c values and relevant Read codes). However, for the purposes of all planned analyses in this and other work-packages, this is a relatively minor issue (except regarding the true non-diabetic hyperglycaemia prevalence rate). For example, the predictors of non-diabetic hyperglycaemia should be consistent across the two analyses (of conservative or more speculative cases) since we would not expect systematic bias in relation to the research questions (i.e. the predictors of non-diabetic hyperglycaemia should be the same whether a large percentage of patients is missed, or not). Even in there is some form of systematic bias (for example if Read code cases are more 'severe'), the findings from the conservative analysis would still be relevant and important. Finally, it might be the case that a conservative approach where we focus on definite non-diabetic hyperglycaemia cases which have been coded as such may be more desirable.

Research question WP 5.2 - What is the effectiveness of the NHS DPP at reducing the conversion of non-diabetic hyperglycaemia to diabetes?

The primary objective of the NHS DPP is to reduce, or at least slow, the rate at which patients with non-diabetic hyperglycaemia go on to develop a full diabetes diagnosis. In line with this, the main outcome in these analyses will be the conversion of non-diabetic hyperglycaemia to diabetes.

Methods: The primary analysis for assessing the effectiveness of the NHS DPP will use the NDA+MDS if assessed as fit for that purpose, otherwise the work will be done in the CPRD. For robustness, we will address the question using two different research designs.

WP 5.2 design 1: We will use all practices participating in the NHS DPP, and compare the conversion rate from non-diabetic hyperglycaemia to diabetes in patients prior to the start of the NHS DPP to the rate afterwards in equivalent patients. To accomplish this, we will match pre-intervention cases of non-diabetic hyperglycaemia ⁹⁷ to post-intervention cases at the same practice and with the same practitioner if possible (excluding cases with a previous diabetes diagnoses). We will then compare the rates of conversion to diabetes within 2 years between these groups.

Earlier, we confirmed that risk-of-diabetes Read codes are already routinely being used. As the NHS DPP-specific Read codes are not available for patients prior to the scheme, we will conduct an initial exercise to identify the group of pre-existing codes that best identify patients classed as eligible using the NHS DPP-specific codes. We will then use the identified codes to classify patients as scheme-eligible both pre- and post-NHS DPP, to ensure comparability. We will use propensity score methods for the matching. In the logistic regression model to calculate the score we will include: age, sex, region, deprivation, QOF comorbidities and all available biological parameters (e.g. body mass index and HbA1c levels at baseline). Data will be complete for all covariates except the biological parameters, for which we expect a very high level of completeness for this group of patients.

Nevertheless, we will use appropriate multiple imputation methods for longitudinal data if needed. 103

We will compare the conversion rates to diabetes between the two matched groups. Since practices are unlikely to refer all their cases of non-diabetic hyperglycaemia to the scheme (because of capacity limits), we will also compare those patients who were referred to their matched pre-intervention controls, while recognising that this comparison will be subject to confounding with any selection bias.

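### WP4 lists sessions attended as a regressor beside provider and patient characteristics, so the stated outcome model does not give the total provider and subgroup differences that RQ 4.4 asks about

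*Protocol*

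**What the plan says.** All references are to the Protocol, Work package 4 - Outcomes, unless stated.

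- **The question.** RQ 4.4 asks "How do outcomes vary by (a) the 4 NHS DPP providers", together with the associated variation in content and delivery, and by patient subgroup.
- **The outcome model (Methods).** The plan is that "we will use multilevel modelling of individual characteristics (focusing on health inequalities – WP1) and service delivery" will be related to outcomes. Service delivery is spelled out there as "service delivery (number of sessions attended; area/provider; and important elements of service delivery identified in WP3". The dependent side is "on the outcomes collected by NDPP providers (weight, HbA1c, WEMWBs etc".
- **Participation as a result.** RQ 4.2 asks "How does service delivery and participation in the programme vary by (a) the 4 NHS DPP providers" and, again, by patient subgroup. The Methods say that regression on patient, provider and service characteristics will serve both participation (4.2) and outcomes (4.4).
- **Who has outcomes.** WP 4.5, Missing data, says of both the face-to-face and the digital dataset that "outcome data was only collected on those who stayed in the programme until the outcomes were recorded".

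For the comparison of providers and patient subgroups, no outcome model without sessions attended is described, and total and direct differences are not distinguished.

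**The concern.** Sessions attended is the dose a person actually took. It builds up after baseline and alongside the weight change being analysed. By the Protocol's own structure it depends on provider and patient factors, since RQ 4.2 makes it a dependent variable. Conditioning on it in the outcome model has two consequences.

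First, any provider or subgroup difference that works through retention is adjusted away. Second, if people who are losing weight keep coming, or if motivation drives both attendance and weight loss, then comparing people with equal attendance across providers compares unlike people. The bias can then exceed the true difference and reverse it.

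WP4 is meant to give providers feedback on performance and to inform conclusions on inequality. A provider that succeeds by keeping people in could look no better, or worse, in the adjusted comparison. A disadvantage that acts through poorer attendance could disappear. With a planned 230,000 individuals, sampling error would be small and such a bias would look precise.

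**Working it through.** The Protocol states no figure on this point, so there is nothing to reproduce. The check has two steps: the structure, from the text, and an illustration with assumed inputs.

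**1. Structure.** RQ 4.2 has provider and patient factors leading to attendance. The outcome model has attendance, provider and patient factors all leading to outcome. Attendance is therefore an intermediate, and a coefficient adjusted for it is not the total difference.

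**2. Illustration (every effect size is an assumption).** Weight change is in kg and negative means loss. Let

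- sessions S = 8 + 2·P − 2·D + a·U + noise (SD 3)
- weight change Y = −0.25·S + c·U + noise (SD 4)

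P is the better-retaining provider, D is deprivation, and U is unmeasured motivation with SD 1. Neither P nor D has a direct effect.

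*Without S in the model*
- Provider: −0.25 × 2 = −0.50
- Deprivation: −0.25 × (−2) = +0.50

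*With S in the model.* Given P, D and S, the leftover influence of U has slope k = a·c / (a² + 3²). The provider coefficient is −2k and the deprivation coefficient is +2k.

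- No motivation effect (a = c = 0): k = 0. Both differences become 0.
- Modest (a = 1, c = −0.5): k = −0.5/10 = −0.05. Provider +0.10, deprivation −0.10.
- Strong (a = 2, c = −1.5): k = −3/13 = −0.23. Provider +0.46, deprivation −0.46.

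A simulation with N = 230,000, sessions rounded and limited to 0–13, agrees. The limits trim the totals slightly.

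| Assumption | Provider, S out | Provider, S in | Deprivation, S out | Deprivation, S in |
|---|---|---|---|---|
| No motivation effect | −0.46 | 0.00 | +0.47 | 0.00 |
| Modest | −0.46 | +0.09 | +0.48 | −0.08 |
| Strong | −0.44 | +0.43 | +0.41 | −0.47 |
| Strong, plus direct effects of 0.2 kg | −0.63 | +0.26 | +0.66 | −0.23 |
| Strong, attendance equal across groups, direct effects of 0.5 kg | −0.50 | −0.50 | +0.52 | +0.51 |

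Hiding needs only that attendance differs between groups and affects the outcome. Reversal in this set-up needs the common cause as well. With equal attendance across groups there is no harm.

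**3. Outcomes seen only in stayers.** Restricting the same simulation to people with 8 or more sessions (an assumed cut-off) gives, for provider with S out and S in: −0.20 and −0.02 (no motivation effect), −0.09 and +0.12 (modest), +0.08 and +0.41 (strong). Leaving S out is nearer the all-participant total each time, but it is still biased, and in the strong case it has the wrong sign.

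**4. Feedback from weight to attendance.** Another illustration lets attendance depend on weight lost so far: 12 sessions, about 70% attendance, 0.2 kg per session, and a provider retaining about 1.5 more sessions, so a total of about 0.2 × 1.5 = 0.3 kg in that provider's favour (here positive means more loss). The session-adjusted difference is about 0 without feedback. With feedback of 0.2 log-odds per kg it runs from −0.13 to −2.25 kg as the assumed between-person SD of weight loss goes from 1 to 5 kg. The sign can reverse, but the size is set by assumptions that the Protocol does not supply.

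**The case against.** The best defence has four parts.

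- **One fixed model is inferred.** The Methods list groups of variables. They do not say that all enter together, or that the adjusted provider coefficient alone answers RQ 4.4. They also say that WP1–3 will shape the choice of variables and that a detailed analysis plan will follow. This stands as a caveat, and a reader should not infer that the Protocol rules out a model without sessions. But sessions attended is named in the text as a regressor beside area/provider, so this is a stated choice and more than a detail left for later.
- **A model without sessions exists.** WP 4.5 is said to contribute to RQs 4.2 and 4.4, and its weight and HbA1c models adjust for baseline scores, provider and CCG. True, but its contrast is face-to-face against digital. It does not cover the four-provider or subgroup differences.
- **Attendance is a legitimate exposure.** WP4 aims to explore drivers of variation, RQ 4.2 reports participation separately, and overall outcomes are described. This stands. The objection is to reading provider and subgroup differences from the session-adjusted coefficients, and studying dose is not in question.
- **Removing the covariate does not cure selection.** Also true, as step 3 shows. WP 4.5 itself acknowledges systematic bias from outcomes limited to those who stayed.

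A reader might extend the point to the digital usage analysis in WP3, which looks at "whether engagement with particular features of the digital DPP (e.g. BCTs) are linked to weight loss outcomes". That does not follow. Engagement is the exposure there, no provider or subgroup contrast is being adjusted, and the wording is exploratory.

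**Conclusion.** The point holds in a limited form. As written, the WP4 outcome model estimates provider and subgroup differences net of attendance, whereas RQ 4.4 asks how outcomes vary by provider and subgroup. The adjusted coefficients lose any part that acts through retention. They can change sign if weight progress or an unmeasured factor drives attendance. This rests on attendance differing between providers or subgroups, which RQ 4.2 treats as a live possibility but the Protocol does not quantify.

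A reader might infer a definite bias in kilograms, or a definite spurious benefit per session. The documents support neither. They give no session effect, no retention difference and no between-person SD, and step 4 shows how far the answer moves with the SD alone. Nor do they support the claim that leaving sessions out yields unbiased differences. It yields a better estimate of the right quantity, among people whose outcomes were recorded.

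**What to change.** In the WP4 Methods:

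1. State that provider and patient-subgroup differences under RQ 4.4 come from a multilevel model with baseline characteristics and area/provider, without sessions attended. Add provider- or site-level content from WP3 where content is the question.
2. Keep attendance as an outcome under RQ 4.2.
3. Report any model that includes sessions attended separately, labelled as an associational dose or mediation analysis. Preferably count sessions up to a fixed milestone and relate them to change after it.
4. State that both models use outcomes seen only in people who stayed, so dropping the covariate does not remove selection on retention. Report retention by provider and subgroup beside the outcome differences.

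The cost is a change of wording and one additional model on the same data. A milestone-based dose analysis would use less of the attendance record.
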